2.3 Clinical Experience

Overall, more than 40 clinical studies with favipiravir have been conducted globally, mainly in the US and Japan. Recently, China has begun studying favipiravir in patients with severe influenza as well as COVID-19. More than 3100 study subjects have received at least one dose of favipiravir manufactured by Toyama Chemical. Favipiravir has been well tolerated in studies in adults and elderly subjects with uncomplicated influenza. A consistent safety profile composed of relatively low frequencies of mild to moderate adverse events (AEs) clustering around the system organ classes of gastrointestinal disorders, investigations, and infections and infestations has been characterized. Mild to moderate transient, asymptomatic elevations in serum uric acid and mild to moderate diarrhea are the two most common AEs known to occur with favipiravir. In double blind studies, the adverse event profile of favipiravir and placebo were similar with the exception of elevations of uric acid. Details can be found in the Investigator’s Brochure.

Favipiravir has been used in an open label study in patients with Ebola, (2400 mg twice eight hours apart, followed by 1200 mg 8 hours later and then 1200 mg BID for the following 9-13 days). Although conclusions about efficacy cannot be reached because of the lack of a concurrent control group, favipiravir at this regimen appeared to be well tolerated. A study in Japan in patients with Severe Fever with Thrombocytopenia administered 1800 mg BID Day 1 followed by 800 mg BID for the next 13 days. It has also been used under compassionate use in patients with rabies or other unusual RNA virus illnesses

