5.3 Removal of Subjects from Treatment

The participation of a subject in the study or the administration of treatment may be terminated at any time for one of the following reasons:

- The subject desires to discontinue study treatment.
- The subject withdraws consent to participate in the study.
- The subject is unwilling or unable to comply with the safety procedures.
- The subject is discovered to be pregnant.
- The subject experiences a medical emergency that necessitates withdrawal.
- The subject is withdrawn at the discretion of the Investigator for medical reasons or non-compliance.
 - AST or ALT > 8 x ULN
 - ALT or AST > 3 x ULN AND total bilirubin > 2X ULN
 - AST or ALT > 3 x ULN AND patient has right upper quadrant pain or eosinophilia

- Uric acid >20mg/dL CrCl < 30

A subject whose treatment is terminated should remain in the study for appropriate follow up assessments whenever possible.

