6.4 Drug Accountability

The Investigator must maintain adequate records showing the receipt, dispensation, or other disposition of favipiravir including the date, quantity and identification of subjects (study ID) who received favipiravir. Drug supplies will be inventoried and accounted. Unused supplies of all favipiravir will be returned to the Sponsor (or designee) or destroyed on site in accordance with local procedures upon approval of the Sponsor.

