7.2 Day 1 (FIRST DOSE AND POST-DOSE)

NOTE: Day 1 is deemed to be the first 24 hours after enrollment into the study, with time 0 (time of first dose) occurring as quickly as possible after the subject's eligibility has been confirmed.

- Administer first dose (1800 mg favipiravir or placebo) at time 0.

Following First Dose:

- Monitor patient for 30 minutes after their first dose.
- Optional: Take a blood sample 45 to 75 minutes following the first dose for post-dose PK analysis

7.3 Days 5, 10, 28 (Follow-up) or Early Termination (Window of +1 or -1 day allowed on Days 5 and 28. Window of -1 allowed for Day 10.)

- Conduct and record the results of a Physical Exam (Day 5, 10, 28).
- Review and record concomitant medications (Note: if there have been changes in concomitant medications during the study, determine whether the change is due to an AE).
- Measure and record vital signs (BP, HR, Temp, Resp).
- Collect and record SPO2 by Finger Sensor
- Collect oropharyngeal swab for virologic testing (RT-PCR) and resistance analysis.
- Collect and record adverse events (see Section 8.4 for detailed instructions).
- Collect nasal swab for antigen testing and molecular viability testing (day 1, 5, 10)
- Collect blood samples for:
 - Hematology and clinical chemistry laboratory analyses (Day 5, 10, 28)
 - Urine for repeat pregnancy test (Day 5)
 - Optional: Antibodies to SARS-CoV-2. (28)
 - Optional: Biobanking (28)
 - Optional: Blood for PK and resistance analysis obtained pre-dose (within 30 minutes prior to dosing) and post-dose (45 to 75 minutes following dosing) (Days 5 and 10).
- Optional: Provide Zymo fecal stool collection kit: one on Day 1, two on Day 10, and 28.

- Optional: Collect stool samples on Day 5, 14, 28, and patient sends in sample at 4 months post enrollment date.

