8.4 Safety Assessments

Abnormal clinical laboratory values that are clinically significant and all reported adverse events will be graded according to the Common Terminology Criteria for Adverse Events (CTCAE) version 5.0.

Safety will be assessed by the collection of observed and reported adverse events, physical exams, vital signs and the following clinical laboratory tests:

- **Hematology**

Hemoglobin (Hgb)	Hematocrit (Hct)
Platelet count	Red blood cell count
White blood cell count with differential	

- **Chemistry**

Blood Urea Nitrogen (BUN)	Creatinine
Total bilirubin	Alkaline Phosphatase
Aspartate transaminase (AST)	Alanine transaminase (ALT)
Gamma-glutamyl transferase (GGT)	Albumin
Glucose	Bicarbonate
Total protein	Sodium
Phosphate	Chloride
Potassium	
Calcium	C-reactive protein
Urate	

NOTES:

- All clinical laboratory assessments listed above (hematology and chemistry) will be conducted at the Stanford University Medical Center clinical laboratory.
- If coagulation assays are ordered as part of the SOC, the results should be added to the EDC.

Including PK and Clinical Laboratory Testing, subjects will undergo up to 7 planned venipunctures during this study.

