8.4.3 Evaluating and Reporting of Adverse Events

All AEs (i.e. a new event or an exacerbation of a pre-existing condition) that occur after dosing with favipiravir and after completion of baseline assessments in the Placebo + SOC arm, must be recorded as an AE or SAE (if applicable), on the Adverse Event eCRF and SAE form, as applicable. The Site Investigator must follow all AEs until the AE resolves, or until the Site Investigator and/or the Medical Monitor determine the event is chronic or clinically stable. If an AE remains unresolved at the conclusion of the study, the Site Investigator and Medical Monitor will make a clinical assessment to determine whether continued follow-up of the AE is warranted. All subjects who have received at least one exposure to study therapy will be evaluated for safety of study treatment.

The Site Investigator should attempt to establish a diagnosis of the event based on signs, symptoms and/or other clinical information. In such cases, the diagnosis should be documented as the AE and not the individual signs/symptoms.

All AEs must be promptly documented on the Adverse Event eCRF and assessed by the Site Investigator. Details of the event must include the dates of onset and resolution, severity, relationship to study drug, seriousness, and whether the event caused the subject to withdraw from the study, outcome and timing with regard to administration of the study drug.

Severity: Severity should be graded and recorded as follows:

- Mild: Awareness of event but easily tolerated
- Moderate: Discomfort enough to cause interference with usual activity

- Severe: Inability to carry out usual activity, incapacitating, requires medical intervention

Relationship: The relationship of the Adverse Event to the study drug will be determined initially by the Site Investigator, and assessed using the following definitions:

- **Related:** There is a distinct temporal relationship between the event onset and administration of the study drug. There is a known reaction to agent or chemical group or predicted by known pharmacology. The event cannot be explained by subject's clinical state or other factors.
- **Unrelated:** Evidence exists that the AE has an etiology other than the study drug (e.g., pre-existing condition, underlying disease, intercurrent illness, or concomitant medication).

Final determination of relatedness will be made by the Sponsor.

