14 SCHEDULE OF ASSESSMENTS

Day	Assessment in the study clinic	Administration of study drugs	Self-collected nasal swab and self-assessment)	Oropharyngeal swab	Blood collected by phlebotomy for clinical labs (CBC, Chem 7, LFTs, uric acid, CRP) ^{A, B}	Blood collected by phlebotomy for biobanking/immunology studies ^C	Blood collected by phlebotomy for PK, pre- and post-dose ^C	Urine for pregnancy test (serum if needed)	Stool self-collected using Zymo fecal kit ^C	Collect nasal swabs for antigen testing	Collect nasal swab for molecular testing
1	X	X	X	X	X	X	X	X	Dispense stool kit	X	X
2		X	X								
3		X	X								
4		X	X								
5	X	X	X	X	X		X	X	X	X	X
6		X	X								
7		X	X								
8		X	X								
9		X	X								
10	X	X	X	X	X		X		Dispense two stool kits	X	X
14			X						X		
21			X								
28	X		X	X	X	X			X, Dispense stool kit		

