Appendix A: Subject Status

A: Blood for uric acid and CRP required at Day 1 while results for CBC/Chem 7/LFTs can be within 48 hours of enrollment

B: Local lab ranges will be submitted by sites for review prior to initiation

C: Collection of biobanking, PK, and stool are optional for sites.

1. ECOG Performance Status

GRADE ECOG PERFORMANCE STATUS

- 0 Fully active, able to carry on all pre-disease performance without restriction
- 1 Restricted in physically strenuous activity but ambulatory and able to carry out work of a light or sedentary nature e.g., light housework, office work
- 2 Ambulatory and capable of all selfcare but unable to carry out any work activities; up and about more than 50% of waking hours
- 3 Capable of only limited selfcare; confined to bed or chair more than 50% of waking hours
- 4 Completely disabled; cannot carry on any selfcare; totally confined to bed or chair
- 5 Dead

2. Study Specific Symptom Status Scale

See symptom survey

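### Section 6.4, followed literally, has the investigator of a double-blind trial record which subjects received favipiravir; on-treatment uric acid is a secondary clue of unknown strength

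*Combined protocol and SAP*

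**What the plan says.** **Drug records.** Section 6.4 requires the investigator to hold records of receipt, dispensing and disposition of favipiravir, including "identification of subjects (study ID) who received favipiravir". The whole section, including its sentence on unused supplies, speaks of favipiravir only.

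**Who judges.** Under Section 8.4.3 the relationship of an adverse event to study drug "will be determined initially by the Site Investigator"; the same section gives the final determination to the sponsor. Section 8.4.2 excludes events of COVID-19 progression from adverse events. Section 5.3 allows treatment or participation to be ended, and one listed reason is "The subject is withdrawn at the discretion of the Investigator for medical reasons or non-compliance".

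**Uric acid.** Section 2.3 says that in double-blind studies "the adverse event profile of favipiravir and placebo were similar with the exception of elevations of uric acid". Section 14 marks the column "Blood collected by phlebotomy for clinical labs (CBC, Chem 7, LFTs, uric acid, CRP" on Days 1, 5, 10 and 28. Section 7.3 likewise lists "Hematology and clinical chemistry laboratory analyses (Day 5, 10, 28", and Section 8.4 includes urate in the chemistry panel. On where samples are run, Section 8.4 says the assessments "will be conducted at the Stanford University Medical Center clinical laboratory", while note B to the schedule says "Local lab ranges will be submitted by sites for review prior to initiation". No passage masks on-treatment uric acid or sends it to a separate reviewer.

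**The concern.** A double blind protects the steps that rest on judgement. In this trial these are the first relatedness call, the sorting of events into COVID-19 progression or adverse event, and the decision to withdraw someone. The first two feed the treatment-emergent adverse event tables in Section 9.7. The third can create missing data, which Section 9.6 imputes as missing at random; withdrawal decided with knowledge of the arm would weaken that assumption.

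Section 6.4 is an operative instruction, not background. If a site follows it as written, the arm is known for certain from the time of dispensing. Uric acid is a weaker matter: it is a possible clue, available only once the Day 5 result is back.

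**Working it through.** The plan states no figure on this point, so there is none to reproduce. The first two steps compare passages; the third is an illustration.

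**Step 1. Does other wording correct Section 6.4, or share its assumption?**

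| Section | Content | Presumes a known arm? |
|---|---|---|
| 6.1 | Matching placebo tablets | No |
| 6.3 | Drug and diary card dispensed in parallel to both arms | No |
| 7.2 | First dose is favipiravir or placebo | No |
| 8.4.6 | SAE follow-up report states whether the blind was broken | No |
| 6.4 | Log of subjects who received favipiravir | Yes |
| 6.5 | Pharmacy provides bottles of favipiravir for outpatient use | Yes |
| 8.4.1 | Length of follow-up after withdrawal for an adverse event refers to the favipiravir arm | Yes |
| 8.4.3 | Adverse event recording starts at a different point in each arm | Yes |

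The plan clearly intends a blind. Nothing in it overrides 6.4, and no unblinded record-keeper is named.

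**Step 2. Who would hold the information?** Section 6.4 names the investigator. Sections 8.4.1 and 8.4.3 have the site investigator document events, seek a diagnosis and make the first causality call. Section 5.3 gives the investigator discretion over withdrawal. I take these to be the same person or site team. That the investigator also decides what counts as COVID-19 progression follows from these duties; Section 8.4.2 does not say so outright.

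**Step 3. How much could uric acid reveal?**

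*Do sites see it?* No sentence says so. It is inferred from the uric acid removal criterion in Section 5.3, the investigator's duty in Section 8.6 to evaluate significantly abnormal results, and the submission of local laboratory ranges.

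*How strong is the clue?* Let d be the mean difference between arms divided by the within-arm SD. Assume one normally distributed value, equal SDs, 1:1 allocation and a cut at the midpoint between the two means. The share of correct guesses is then Φ(d/2).

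| Assumed d | Φ(d/2) | Correct guesses |
|---|---|---|
| 0.5 | Φ(0.25) | 60% |
| 1 | Φ(0.5) | 69% |
| 2 | Φ(1.0) | 84% |
| 3 | Φ(1.5) | 93% |

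Chance is 50%. Every value of d is an assumption, because the documents give neither a mean shift nor an SD. The formula also favours the guesser, since a site would not know the best cut-off.

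**The case against.** **The log is probably template residue.** A blinded investigator cannot record who received favipiravir without the code, and the protocol carries other leftovers, such as study infusion in Section 9.7 and compassionate treatment in Section 12.2. Randomization notification and study drug requests are left to the MOP (Section 3.2), and dispensing to pharmacy instructions (Section 6.5); neither is among the documents. This is a fair account of how the wording arose, and safeguards may exist elsewhere. It does not change the fact that 6.4 is current text that a site is told to follow.

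**The consequences are partly contained.** The sponsor makes the final relatedness determination, although the sponsor's own blinding is not described. Subjects whose treatment is stopped should remain in follow-up under Section 5.3, so only full study withdrawal loses home swabs, and Section 9.6 plans sensitivity analyses on missingness. The primary endpoint is RT-PCR on self-collected swabs. All of this stands and limits the exposure.

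**Uric acid.** A reader might infer that comparing the Day 1 and Day 5 values reveals the arm with high probability. Assuming a rise of 2 to 4 mg/dL and an SD of change of 0.8 to 1.2 mg/dL, the same formula gives about 80% to 99%. The documents supply neither input, and Section 2.3 describes the elevations only as mild to moderate and transient. With a rise of 0.5 mg/dL and an SD of 1.2 mg/dL the figure is 58%. Masking a safety analyte is also a real trade-off: withholding every value below the removal limit would conflict with Section 8.6, and might have to work across several laboratories. This objection largely stands, so the uric acid part is optional.

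**Conclusion.** The point holds for Section 6.4. As written, the accountability rule breaks the blind for the person making the first safety judgements, and it should be corrected together with the matching wording in 6.5, 8.4.1 and 8.4.3. Its effect cannot be put as a number: followed literally, the log identifies the arm with certainty; if sites already log blinded kits, it reveals nothing and only the text is wrong.

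The uric acid matter is secondary. It rests on the inference that sites see on-treatment values and on assumed shifts of 0.5 to 3 SD, which give about 60% to 93% correct guesses.

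The exposure is confined to initial relatedness, COVID-19 versus adverse event attribution, and full study withdrawal. A reader might go further and infer that the primary comparison is compromised, or that participants learn their arm from laboratory results. The documents support neither: the primary reading is an objective laboratory result, and no passage says that uric acid results reach participants.

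**What to change.** **Needed.**
- Reword Section 6.4 to account for study drug (favipiravir or matching placebo) by blinded bottle or kit number, for all participants and for returned supplies.
- Reconcile Sections 6.5, 8.4.1 and 8.4.3 so that dispensing, follow-up after withdrawal for an adverse event, and the start of adverse event recording can be applied without knowing the arm. The content of those rules is for the clinical team.
- If the MOP or pharmacy instructions already hold blinding safeguards, add a cross-reference.

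The cost is a few sentences in an amendment, with no change to design, sample size or analysis.

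**Optional.** Consider limiting who sees uric acid on Days 5 and 10. Any such step must leave the protocol's existing limit unchanged and preserve the investigator's Section 8.6 duty to evaluate and follow abnormal results. The cost is more than a report setting: urate sits in the general chemistry panel, up to 5 sites may take part, local laboratories may be involved, and an alert above the limit would itself be a clue to the arm. Leaving the values visible, with the reason stated, would also be defensible.

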Appendix A: Subject Status

A: Blood for uric acid and CRP required at Day 1 while results for CBC/Chem 7/LFTs can be within 48 hours of enrollment

B: Local lab ranges will be submitted by sites for review prior to initiation

C: Collection of biobanking, PK, and stool are optional for sites.

1. ECOG Performance Status

GRADE ECOG PERFORMANCE STATUS

- 0 Fully active, able to carry on all pre-disease performance without restriction
- 1 Restricted in physically strenuous activity but ambulatory and able to carry out work of a light or sedentary nature e.g., light housework, office work
- 2 Ambulatory and capable of all selfcare but unable to carry out any work activities; up and about more than 50% of waking hours
- 3 Capable of only limited selfcare; confined to bed or chair more than 50% of waking hours
- 4 Completely disabled; cannot carry on any selfcare; totally confined to bed or chair
- 5 Dead

2. Study Specific Symptom Status Scale

See symptom survey
